### Exclusion Criteria

- Inability to complete physical function assessment or inability to do a chair stand without using hands.
- Use of antidiabetic medications
- Use of testosterone supplement or replacement
- Clinical disorder precluding/interfering with participation or assessments
  - Unstable angina, arrhythmia, uncontrolled hypertension
  - End Stage Renal Disease on Hemodialysis
  - Lower extremity amputation or paralysis
  - Neurological conditions causing functional or pronounced cognitive impairments
  - Active malignancy except for non-melanomatous skin cancers
- Unable to provide consent
- Weight instability (defined as gain or loss of  $\geq$ 10% body mass over the last 6 months)

## Subject Recruitment and Compensation

- Describe recruitment procedures, including who will introduce the study to potential subjects. Describe how you will ensure that subject selection is equitable and all relevant demographic groups have access to study participation (per 45 CFR 46.111(a) (3)). Include information about approximately how many DUHS subjects will be recruited. If subjects are to be compensated, provide specific prorated amounts to be provided for expenses such as travel and/or lost wages, and/or for inducement to participate.

Participants will be recruited from outpatient Geriatrics, Endocrinology and Primary Care clinics serving Duke Health using Duke Office of Clinical Research, Research Innovation Center, Maestro Care recruitment tool, and from the Duke Health and Exercise Research Registry.

We will use the Duke Office of Clinical Research, Research Innovation Center, Maestro Care recruitment tool to identify potentially eligible patients in Duke Health geriatric medicine, endocrinology and primary care clinics. Using the Maestro Care electronic medical record, we will identify and invite older patients with prediabetes to be a part of our study. For any subject for which the study team and associates

do not have an established prior relationship, the patient's research contact preference will be noted and no contact will be made with those individuals with an opt-out status. Finally, we will check against the "banner" in MaestroCare to verify whether or not the patient has opted out for being contacted.

Clinicians in the geriatric medicine and primary care clinics may also refer potential subjects.

In addition, we will use the Duke Health and Exercise Research Registry.

The Duke Health and Exercise Research Registry was developed in April 2019 and is a registry of persons interested in exercise-related research studies. There are 4035 persons registered with a signed consent, contact information, and health information available for screening. Of these 4035, there are 600+ individuals who are  $\geq 60$  years; there are an additional 716 individuals with missing age, that would be included on the study invitation list, which would include over 1000 person's total.

We will recruit 30 sedentary adult men and women ages  $\geq 60$  including  $\sim 30\%$  non-white participants.

Participants will receive \$30 after the initial assessment and another \$50 after the endpoint assessment and semi-structured interview.

### Consent Process

- Complete the consent section in the iRIS Submission Form.

### Subject's Capacity to Give Legally Effective Consent

- If subjects who do not have the capacity to give legally effective consent are included, describe how diminished capacity will be assessed. Will a periodic reassessment occur? If so, when? Will the subject be consented if the decisional capacity improves?

Only subjects able to give legally effective consent will be enrolled.

### Study Interventions

- If not already presented in #4 above, describe study-related treatment or use of an investigational drug or biologic (with dosages), or device, or use of another form of intervention (i.e., either physical procedures or manipulation of the subject or the subject's environment) for research purposes.

### Risk/Benefit Assessment

- Include a thorough description of how risks and discomforts will be minimized (per 45 CFR 46.111(a) (1 and 2)). Consider physical, psychological, legal, economic and social risks as applicable. If vulnerable populations are to be included (such as children, pregnant women, prisoners or cognitively impaired adults), what special precautions will be used to minimize risks to these subjects? Also identify what available alternatives the person has if he/she chooses not to participate in the study. Describe the possible benefits to the subject. What is the importance of the knowledge expected to result from the research?

There is minimal risk to the participants. Exercise testing and training is used extensively for research and clinical purposes with minimal risk to participants. The Vivo program is led by certified trainers and carefully designed to ensure maximum safety. Participants will be instructed to only do the activities they feel comfortable doing and will be asked to provide their rate of perceived exertion multiple times throughout the

exercise class to allow for close monitoring. The minimal risk to human participants in this study is greatly outweighed by potential health benefits that may accrue participants and by the importance of the scientific knowledge that may reasonably be expected to result from this work.

### Costs to the Subject

- Describe and justify any costs that the subject will incur as a result of participation; ordinarily, subjects should not be expected to pay for research without receiving direct benefit.

There will be no additional costs to the subjects.

### Data Analysis & Statistical Considerations

- Describe endpoints and power calculations. Provide a detailed description of how study data will be analyzed, including statistical methods used, and how ineligible subjects will be handled and which subjects will be included for analysis. Include planned sample size justification. Provide estimated time to target accrual and accrual rate. Describe interim analysis including plans to stop accrual during monitoring. Phase I studies, include dose escalation schema and criteria for dose escalation with definition of MTD and DLT.

A) Qualitative - To explore concepts related to a complex process (barriers, acceptability, and retention of a health behavior) the team will employ a qualitative analytical approach. Drs. [name] and [name] will use applied thematic analysis, organizing the data in response to the a priori questions contained in the semi-structured interviews and interview guides. Audio recordings will be transcribed verbatim following a transcription protocol. [name] and [name] will use NVivo 12 software to develop and apply structural (a priori) codes to segment participants' narratives into conceptual categories (e.g., all text describing a similar concept, such as psychosocial factors). Next, analysts will identify and apply content-driven (emergent) codes to the text for each of the conceptual categories (e.g., potential themes related to psychosocial factors). Inter-coder reliability assessments will be conducted on approximately 25% of transcripts during both structural and content coding. Discrepancies in coding will be resolved through analyst discussions; transcripts will be re-coded, and the codebook revised accordingly. Once coding is complete, we will examine code frequencies across transcripts to identify salient factors for each interview, followed by comparing and contrasting factors between interviews. The team will complete analytical memos describing the factors influencing success in adherence, usefulness and impact of Vivo on function and QOL, together with illustrative quotes for each.

B) Quantitative - In this single-arm feasibility study with pre- and post-assessment (baseline and 12 weeks) we will use descriptive statistics to summarize the distribution of the covariates and dependent variables, and student t-tests to compare pre- and post-outcomes. These analyses are designed to support the feasibility of executing the fully powered randomized trial in Phase II. Primary outcome will be number of full stands that can be completed in 30 seconds with arms folded across chest. The 30-second has excellent test-retest reliability ( $r = 0.89$ , 95% CI = 0.79-0.93) and criterion validity compared to weight adjusted leg press ( $r = 0.77$ , 95% CI = 0.64-0.85). Additional outcomes include Balance component of the SPPB; 2-minute step test for aerobic endurance; 8-ft Timed Up and Go; 3-day food records; Waist Circumference; Perceived social support and Self-efficacy; Quality of Life Short Form Health Survey 36 (SF-36); Profile of mood state (POMS); Center for Epidemiologic Studies Depression Scale (CES-D); Perceived Stress Scale (PSS); Satisfaction with Life scale (SWL).

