## Research Abstract

Please type your Research Abstract here:

The Research Abstract should summarize the main points of your study in one paragraph. The following guidelines may help you:

1. Purpose and objective (1-2 sentences)
2. Study activities and population group (2-4 sentences)
3. Data analysis and risk/safety issues (1-2 sentences)

Aim: Evaluate the acceptability, feasibility, and fidelity of current Vivo prototype in sedentary older adults with prediabetes

This will be a 12-week single arm feasibility study using the currently available Vivo prototype. After informed consent and baseline assessments, 24 individuals will be enrolled in cohorts of 5-6 people. Each cohort will meet virtually twice a week with their small group and certified trainer for 45 minutes.

Participants will be men and women,  $\geq 60$  years old, sedentary, with prediabetes and low function. All participants will complete a pre- and post-intervention virtual physical function assessment, 3-day food record, height, weight, waist circumference, and social support, self-efficacy, and psychosocial functioning questionnaires. At 12-weeks, semi-structured interviews will be conducted to assess acceptability, usability and satisfaction.

In this single-arm feasibility study with pre- and post assessment (baseline and 12 weeks) we will use descriptive statistics to summarize the distribution of the covariates and dependent variables, and student t-tests to compare pre- and post-outcomes. These analyses are designed to support the feasibility of executing the fully powered randomized trial in Phase II. Table 2 summarizes all outcome measures. Qualitative interviews will be used to explore concepts related to barriers, acceptability, and retention of the health behaviors.

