## Research Summary

### State your primary study objectives

Evaluate the acceptability, feasibility, and fidelity of current Vivo prototype in sedentary older adults with prediabetes.

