### State your secondary study objectives

Access feasibility of intervention delivery.

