## Standard Research Summary

### Purpose of the Study

- Objectives & hypotheses to be tested

Evaluate the acceptability, feasibility, and fidelity of current Vivo prototype in sedentary older adults with prediabetes

1: Assess a) attendance, benefits and barriers/facilitators of participation; b) ease of use; and c) overall satisfaction.

2: Assess trainer fidelity.

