Why don't older adults participate in strength training exercise? Older adults report not participating in resistance training due to lack of age appropriate programs, fear of a gym setting, poor access to a gym, joint and other kinds of pain, and lack of social support. These barriers have been compounded as a result of COVID-19, wherein older adults are encouraged to socially isolate, leading to even less physical activity.

Especially relevant today during the Covid pandemic, population-based studies show that socially isolated and lonely older adults have a 59% higher risk of physical and mental health decline. Vivo addresses these major barriers to carrying out strength training with the social support and ease of use factors leading to our product's popularity during the pandemic last year (The New York Times, December 14, 2020). Vivo trainers deliver strength training instruction and coaching through an interactive online training session incorporating social support and social engagement. Vivo is a monthly membership based online resistance training program where small groups (families, friends, couples) work with a trainer for 45 minutes 2-3 times/week on building strength, flexibility, balance, and cognitive skills. Typically, there is a maximum of 6 participants per group. Classes are structured and designed to measure progress and provide custom feedback to all users.

Other than the live classroom experience via Zoom the current Vivo prototype does not have interactive dashboard capability. Feedback about performance and resistance training outcomes are all recorded manually and discussed over Zoom with the trainer at each session. To date since the onset of the pandemic in March 2020, 92 people have participated in Vivo (age range 44-93). We conduct baseline and 8-week functional assessments on all participants. Even with the technological limitations we found excellent proof of concept in our small pilot study of 34 older adults (74% women; mean age 70.9 y; range 60-84y) after 8 weeks of participating in Vivo with a certified trainer (average of 12 hours of training per person). We observed:

- +25.8% improvement in upper body strength as measured by the 30 second arm curl test
- +25.9% improvement in lower body strength as measured by the 30 second chair stand test
- +28% improvement in endurance as measured by the 2-minute knee raise test

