## Design & Procedures

- Describe the study, providing detail regarding the study intervention (drug, device, physical procedures, manipulation of the subject or the subject's environment, etc.). Discuss justifications for placebo control, discontinuation or delay of standard therapies, and washout periods if applicable. Identify procedures, tests and interventions performed exclusively for research purposes or more

frequently than standard of care. Include alternative therapies, concurrent therapies discontinued per protocol, risk benefit ratio, and use of tissue/specimens. Discuss monitoring during washout periods if applicable. Include brief description of follow-up, if any.

This will be a 12-week single arm feasibility study using the currently available Vivo prototype to assess 1) adherence and retention, 2) acceptability and satisfaction with Vivo, 3) technology useability (i.e., Zoom, email), and 4) change in physical function in sedentary older adults with prediabetes and lower function.

**Remote Consent:** The study informational session is done one-on-one via a scheduled ZOOM meeting appointment with study staff. The secured REDCap platform will be used to obtain the participants' electronic consent (eConsent).

After informed consent and baseline assessments, 30 individuals will be enrolled in cohorts of 5-6 people.

Physical Function, Activity, and Diet Outcomes (baseline and week 12)	
Physical measurements	Height, weight, and waist circumference
30-second chair stands to quantify lower body strength	Number of full stands that can be completed in 30 seconds with arms folded across chest
Short Physical Performance Battery to quantify balance, lower extremity strength	Balance (side-by-side, semi-tandem, tandem), strength (time to complete 5 chair stands).
Gait speed tests	Number of seconds required to walk 4 meters
2-minute step test to measure aerobic endurance	Number of full steps completed in 2 minutes, raising each knee to a point midway between the patella (kneecap) and iliac crest (top hip bone)
8-ft Up and Go to assess agility/dynamic balance	Number of seconds required to get up from a seated position, walk 8 feet (2.44 m), turn, and return to seated position
30-second arm curl to quantify upper body strength	Number of arm curls completed in 30 seconds
Social Support and Self-efficacy	

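### The only named primary outcome is chair stands, and the quantitative plan lists no attendance, adherence or retention outcome, although the trial's objectives are acceptability, feasibility and fidelity

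*Combined protocol and SAP*

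**What the plan says.** All places are in the combined protocol and SAP.

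- **Objectives.** Under Research Summary the primary objective is to "Evaluate the acceptability, feasibility, and fidelity of current Vivo prototype in sedentary older adults with prediabetes", and the secondary objective reads "Access feasibility of intervention delivery". Neither names physical function.
- **Purpose of the Study.** There are two numbered aims: "1: Assess a) attendance, benefits and barriers/facilitators of participation; b) ease of use; and c) overall satisfaction" and "2: Assess trainer fidelity".
- **Design & Procedures.** The study is to "assess 1) adherence and retention, 2) acceptability and satisfaction with Vivo, 3) technology useability (i.e., Zoom, email), and 4) change in physical function". The unlabelled outcome table that follows covers physical function and measurements, social support and self-efficacy, and psychosocial functioning.
- **Data Analysis & Statistical Considerations, B) Quantitative.** After descriptive statistics and pre/post t-tests, the plan says "Primary outcome will be number of full stands that can be completed in 30 seconds with arms folded across chest". The additional outcomes are function tests, food records, waist circumference and psychosocial scales.
- **Data Analysis & Statistical Considerations, A) Qualitative.** Barriers, acceptability and retention are explored through coded interviews. Design & Procedures says the 12-week interviews address acceptability, usability and satisfaction.
- **Research Abstract.** It states "Table 2 summarizes all outcome measures". No table in the text reviewed carries that label.

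**The concern.** A pre/post comparison of chair stands says whether function changed in those measured twice. It does not say how many sessions people attended or how many stayed to week 12. Followed as written, the result labelled primary would therefore not answer the question the trial sets itself. The figures that would answer the quantitative part of that question have no named variable, denominator or summary. The same section says the analyses are meant to support the feasibility of a randomized Phase II trial, yet it specifies no feasibility quantity. What is at stake is a report whose headline concerns function while the feasibility figures are defined after the data are seen.

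**Working it through.** The plan gives no power, effect size, SD or sample-size derivation for any outcome, so it has no figure to reproduce. The main check is textual.

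**Step 1. Trace each stated target to a measure.**

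| Target | Where stated | In the quantitative outcome list or outcome table? | Elsewhere? |
|---|---|---|---|
| Attendance, adherence | Purpose of the Study; Design & Procedures | No | Participation information at Vivo is mentioned under External Personnel, with no variable defined; adherence is an interview theme |
| Retention | Design & Procedures | No | Interview theme only |
| Acceptability, usability, satisfaction | Objectives; Purpose of the Study; Design & Procedures | No | Yes, 12-week interviews |
| Trainer fidelity | Objectives; Purpose of the Study | No | No instrument, rater or summary found |
| Physical function | Design & Procedures; arguably benefits in aim 1 | Yes, and named primary | Not applicable |

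The one target named primary is absent from both formal objectives. Attendance, adherence and retention, which are naturally reported as proportions, have no defined outcome.

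**Step 2. What the two feasibility proportions could show.** Scheduled sessions per participant: 12 x 2 = 24. For retention of x out of n, the exact 95% limits are the 0.025 quantile of Beta(x, n - x + 1) and the 0.975 quantile of Beta(x + 1, n - x). The protocol gives both 24 and 30 as the number enrolled, so both are shown. The retention counts are assumed.

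- 24/30 = 80%: 61.4% to 92.3%
- 27/30 = 90%: 73.5% to 97.9%
- 19/24 = 79%: 57.8% to 92.9%

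For mean attendance, the half-width is t(0.975, n - 1) x SD / sqrt(n). With an assumed between-person SD of 20 to 30 percentage points, this is 7.5 to 11.2 points at n = 30 and 8.4 to 12.7 points at n = 24. These intervals ignore clustering by exercise cohort.

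**Step 3. Why the denominator must be stated (illustration on assumed inputs).** Suppose 24 of 30 complete and attend 90% of sessions, and six leave early having attended 90% until then. Completers contribute 24 x 0.90 = 21.6.

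- Leaving after week 2 (4 sessions offered): 6 x (4 x 0.90 / 24) = 0.90; (21.6 + 0.90) / 30 = 75.0%
- Leaving after week 3 (6 offered): 6 x (6 x 0.90 / 24) = 1.35; (21.6 + 1.35) / 30 = 76.5%
- Leaving after week 6 (12 offered): 6 x (12 x 0.90 / 24) = 2.70; (21.6 + 2.70) / 30 = 81.0%

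Among completers, or counted only up to withdrawal, the same data give 90%. The gap from definition alone is 9 to 15 points.

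**Step 4. Chair stands as a secondary outcome.** The 95% half-width for mean change is t(0.975, n - 1) / sqrt(n) in SD units: 0.37 SD at n = 30 and 0.42 SD at n = 24, with no dropout. The protocol gives no SD of change, so this cannot be put into stands.

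**The case against.** The strongest reply concerns what the word primary covers. The sentence stands under B) Quantitative, directly after the t-tests, and may rank only the pre/post measures. The qualitative plan comes first and deals with acceptability, barriers and adherence. That reading is reasonable, and on it the label is ambiguous rather than contradictory. It does not supply the missing outcomes: interviews give no attendance or retention proportion, and the quantitative list names none. Descriptive statistics on dependent variables could take in attendance, but nothing says so.

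Table 2 may also define feasibility outcomes. The unlabelled table under Design & Procedures is the obvious candidate. Its first block is headed for activity and diet as well as function, yet shows no activity or diet row, so it may be incomplete as read. This limits certainty about what is absent.

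Several stronger readings are tempting, and the documents do not support them:

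- That function ranks last because it is fourth in the design list. No section says the order is a ranking, and function is a stated purpose.
- That acceptability goes unmeasured. The interviews cover it.
- That Vivo's participation data may only be correlated with study data. The External Personnel section gives a purpose for sharing; it sets no limit on analysis.
- That Phase II hinges on the chair-stand test. No section says so, and no progression threshold is set.

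**Conclusion.** The point stands as a mismatch between the objectives and the quantitative outcomes. The only outcome named primary measures function, and no attendance, adherence or retention outcome is listed, on either reading of primary. The study can still run, but the plan should be corrected before the data are analysed. Confidence is moderate, because Table 2 cannot be identified.

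A reader might take the 9 to 15 point attendance gap as a measured error in the plan. It is not: retention, attendance and leaving times are all assumed, and no specified decision depends on it. It shows only that the definition matters. The missing trainer-fidelity measure and the conflicting enrolment figures (24 in the Research Abstract; 30 in Design & Procedures and in the recruitment section) are secondary points to clarify.

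**What to change.** In B) Quantitative:

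1. Name as primary quantitative feasibility outcomes (a) the proportion of the 24 scheduled sessions attended per enrolled participant and (b) the proportion of all enrolled participants who complete the week-12 assessment. Report each on the all-enrolled denominator with a 95% CI, and state how sessions after withdrawal and cancelled sessions are counted.
2. Keep chair stands as the lead secondary outcome, for function, reported as mean change with SD and CI.
3. State that acceptability, usability and satisfaction are answered by the interview analysis.
4. If Table 2 already defines feasibility outcomes, cite it and make the primary-outcome sentence agree with it.

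Separately, say how trainer fidelity will be assessed or where that is defined, and reconcile the enrolment number.

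**Cost.** The change is mostly wording, with no new visits or participant burden. Three downsides should be accepted openly:

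- Session attendance must be obtained from Vivo, which delivers the intervention and is the primary grantee (Sponsor and Funding Source). The External Personnel section describes data going to Vivo and no return flow. The background section reports an "average of 12 hours of training per person" among earlier users, which suggests such records can be supplied but does not establish it.
- The retention interval will be wide and may often fail to separate adequate from inadequate retention.
- Attendance and retention do not measure acceptability or fidelity, so they answer only part of the primary objective.
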